## 5.2 Protocol deviations

Protocol deviations are failures to adhere to the inclusion/exclusion criteria and protocol requirements. Important protocol deviations are a subset of protocol deviations that may significantly impact the completeness, accuracy, and/or reliability of key study data or that may significantly affect a participant's rights, safety, or well-being. Protocol deviations (PDs) will be classified into key PDs (important) and non-key PDs. Key PDs that lead to participant/sample exclusion from the immunogenicity analyses will be identified and provided for incorporation into the analysis datasets prior to database lock.

All PDs will be assessed and documented prior to releasing the database. Depending on the nature of the key PD, either the whole participant data might be excluded from the analysis sets (i.e., for key deviations on ICF), or only the data collected after the key PD

occurred might be excluded (e.g., for use of prohibited concomitant medications during the trial).

### 5.3 Subgroups

Subgroup analysis may be performed for certain CCI endpoints based on N-binding antibody status at pre-Dose 1.

## 6 STATISTICAL ANALYSES

### 6.1 General considerations

In general, all the data summaries will be performed by the following treatment groups:

Age Strata	Cohorts	Treatment Group Description
$\geq 18$ years	3a, 3b	Dose 1: BNT162b2 (WT/OMI BA.4/5) 30 $\mu$ g + BNT162b4 15 $\mu$ g, Dose 2: BNT162b2 (OMI XBB.1.5) 30 $\mu$ g + BNT162b4 15 $\mu$ g ( $\geq 18$ y)
	4a, 4b	Dose 1: BNT162b2 (WT/OMI BA.4/5) 30 $\mu$ g + BNT162b4 30 $\mu$ g, Dose 2: BNT162b2 (OMI XBB.1.5) 30 $\mu$ g + BNT162b4 30 $\mu$ g ( $\geq 18$ y)
	1, 2, 3a, 3b, 4a, 4b	BNT162b2 (WT/OMI BA.4/5) one dose only ( $\geq 18$ y)
18-55 years	1	Dose 1 and Dose 2: BNT162b2 (WT/OMI BA.4/5) 30 $\mu$ g + BNT162b4 5 $\mu$ g (18-55y)
	2	Dose 1 and Dose 2: BNT162b2 (WT/OMI BA.4/5) 30 $\mu$ g + BNT162b4 10 $\mu$ g (18-55y)
	3a	Dose 1: BNT162b2 (WT/OMI BA.4/5) 30 $\mu$ g + BNT162b4 15 $\mu$ g, Dose 2: BNT162b2 (OMI XBB.1.5) 30 $\mu$ g + BNT162b4 15 $\mu$ g (18-55y)
	4a	Dose 1: BNT162b2 (WT/OMI BA.4/5) 30 $\mu$ g + BNT162b4 30 $\mu$ g, Dose 2: BNT162b2 (OMI XBB.1.5) 30 $\mu$ g + BNT162b4 30 $\mu$ g (18-55y)
	1, 2, 3a, 4a	BNT162b2 (WT/OMI +BA.4/5) 30 $\mu$ g one dose only (18-55y)
	5	Dose 1 and Dose 2: BNT162b4 30 $\mu$ g (18-55y)
>55 years	3b	Dose 1: BNT162b2 (WT/OMI BA.4/5) 30 $\mu$ g + BNT162b4 15 $\mu$ g, Dose 2: BNT162b2 (OMI XBB.1.5) 30 $\mu$ g + BNT162b4 15 $\mu$ g ( $>55$ y)
	4b	Dose 1: BNT162b2 (WT/OMI BA.4/5) 30 $\mu$ g + BNT162b4 30 $\mu$ g, Dose 2: BNT162b2 (OMI XBB.1.5) 30 $\mu$ g + BNT162b4 30 $\mu$ g ( $>55$ y)
	3b, 4b	BNT162b2 (WT/OMI BA.4/5) 30 $\mu$ g one dose only ( $>55$ y)
	1, 2, 3a, 3b, 4a, 4b, 5	All participants

“All participants” will be presented in disposition, baseline, and selected safety summary tables as specified.

No formal statistical comparisons between vaccine dose levels will be performed. Missing data, other than that described for AEs/Concomitant Medications/Vaccinations below will not be imputed.

### 6.1.1 General methods

In general, continuous variables will be summarized using the following descriptive statistics: number of participants (n), mean, standard deviation (SD), median, minimum (min) and maximum (max).

For the assay results geometric means (GMs) and geometric mean fold rises (GMFRs) will be calculated.

The GMs will be calculated as the mean of the assay results after making the logarithm transformation and then exponentiating the mean to express results on the original scale. 2-sided 95% confidence intervals (Cis) will be obtained by taking log transforms of assay results, calculating the 95% CI with reference to the Student's t distribution, and then exponentiating the confidence limits.

GMFRs are defined as ratios of the results post-dose to the results before dose of IMP. GMFRs are limited to participants with non-missing values at both timepoints.

GMFRs will be calculated as the mean of the difference of logarithmically transformed assay results (later timepoint minus earlier timepoints) and exponentiating the mean. The associated 2-sided 95% CIs will be obtained by constructing CIs using the Student's t distribution for the mean difference on the logarithmic scale and exponentiating the confidence limits.

Categorical variables will be summarized by presenting absolute and relative frequencies (n and %) of participants in each category and the number of participants with missing data ('missing' category will be presented if there is one or more missing value).

For event-driven occurrence data (e.g., adverse event, concomitant medication.), the percentages will be calculated as the number of participants reporting each event over number of participants in the analysis set (N). Unless otherwise noted, also for reported visit data (e.g., clinical laboratory.) the percentages will be calculated on the participant-level, e.g. number of participants in the sentinel cohort only.

The rates of binary endpoints such as primary safety variables (local reactions and systemic events) and seroresponse will be provided by treatment group along with the corresponding 2-sided 95% exact CIs using the [Clopper-Pearson method](#).

All critical data collected during the trial will be listed, the trial day to the first dose and /or the relative day to the last dose will be presented as appropriate. The data will be sorted by treatment group, participant number and date of assessment (if applicable).

Unless otherwise noted, unscheduled assessments will be listed only and not included in the by-visit summaries/analysis. Windowing of data for the purposes of assigning to a visit will occur as per Section [6.1.3](#).

### 6.1.2 General definitions

**Baseline** is defined as last available value prior to first dose of trial IMP. The same baseline definition will be used for the calculation of GMFR and seroresponse and for the clinical laboratory and 12-lead ECG shift from pre-Dose 1 to post-Dose 1 and post-Dose 2 visits unless otherwise specified.

**Change from baseline:** Unless otherwise specified, this will be calculated as follows:

Change from baseline = post-baseline assessment value – baseline assessment value.

If either the baseline or post-baseline assessment value is missing, the change from baseline is set to missing as well.

**Body mass index (BMI)** will be calculated as follows:

$$\text{BMI } \left( \frac{\text{kg}}{\text{m}^2} \right) = \frac{\text{Weight (kg)}}{\text{Height(m)}^2}$$

**Temperatures collected in degrees Fahrenheit** will be converted to degrees Celsius using  $(^{\circ}\text{F} - 32) \times 5/9$  and grading will be based on the unrounded conversions.

**Duration** will be calculated as follows:

- Duration = last observation date – first observation date + 1.

For conversion of days to months or years, the following rules will be applied:

- 1 month = 30.4375 days
- 1 year = 365.25 days

**Trial day** will be calculated as follows:

- Trial day:
  - If assessment date < treatment start date, then trial day = assessment date – date of Dose 1
  - If assessment date  $\geq$  treatment start date, then trial day = assessment date – date of Dose 1 + 1

That is, trial day 1 indicates the date of treatment initiation.

### 6.1.3 Analysis visit

Study data are reported according to SoAs detailed in Table 3 and Table 7 in the CTP. The analysis visits of data will be based on the visits reported and validated in the electronic data capture (EDC) system.

If multiple valid non-missing observations exist in an analysis window for a specific visit, a single value will be chosen in the by-visit summary analyses based on the following rules:

For baseline,

- the last available records prior to the date and time of the first dose of IMP will be selected. Data reported at visit “Pre-Dose 1” on the same day of IMP Dose 1 administration will be taken as prior to IMP Dose 1.

For post-baseline visits,

- If the analysis values are numeric and the toxicity grades are available, the record with the highest toxicity grade will be selected.
- If the analysis values are numeric and the toxicity grades are identical or not available, the average (arithmetic mean) will be used.
- If the analysis values are categorical, the most conservative value will be selected (e.g., abnormal will be selected over normal).

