9.4.1 General considerations

In general, data will be summarized by DL.

Categorical variables will be summarized presenting absolute and relative frequencies (n and %) of subjects in each category.

Continuous variables will be summarized using the following descriptive statistics: number of subjects (n), mean, standard deviation, median, minimum, and maximum.

Analysis of antibody titers will be performed on natural log scale and the results will be exponentiated back to original scale.

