9.4.3 Secondary immunogenicity endpoints

The secondary endpoints are defined in Sections [3](#) and [13.6](#).

Cohorts 1 to 4

Geometric mean titers (GMTs) of SARS-CoV-2 ancestral strain and Omicron neutralizing antibody with associated 95% confidence interval (CI) will be calculated at each timepoint as the mean of the assay results after making the logarithm transformation and then exponentiating the mean to express results on the original scale. Two-sided 95% CIs will be obtained by taking log transformations of assay results, calculating the 95% CI with reference to the Student t distribution, and then exponentiating the confidence limits.

Geometric mean fold rises (GMFR) of SARS-CoV-2 ancestral strain and Omicron neutralizing antibody with associated 95% CI will be calculated at each timepoint. GMFRs are defined as ratios of the results after vaccination to the results before vaccination (pre-Dose 1). GMFRs will be calculated as the mean of the difference of logarithmically transformed assay results (later timepoint minus earlier timepoint) and exponentiating the mean. The associated 2-sided 95% CIs will be obtained by constructing CIs using the Student t distribution for the mean difference on the logarithm scale and exponentiating the confidence limits.

Seroresponse is defined as achieving ≥ 4 -fold rise from baseline (pre-Dose 1). If the baseline measurement is below lower limit of quantitation (LLOQ), the postvaccination measure of $\geq 4 \times \text{LLOQ}$ is considered seroresponse. The counts, percentages and associated Clopper-Pearson 95% CI of subjects with seroresponse at each timepoint will be provided.

Further details of the secondary immunogenicity analyses will be described in the SAP.

CCI

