**6.6 Immunogenicity analyses**

The neutralizing antibody titers above the lower limit of quantitation (LLOQ) are considered accurate and their quantitated values will be reported. Neutralizing antibody titers below the LLOQ will be set to  $0.5 \times$  LLOQ for all the analysis if not specified otherwise. Missing data will not be imputed.

Only participants without breakthrough SARS-CoV-2 infections (without positive central or local NAAT from pre-Dose 1 through the visit) will be analyzed for the respective visit.

The number of participants with blood samples drawn at each visit and their respective time windows as specified in [Table 4](#) will be summarized for the Safety Set.

[Table 7](#) and [Table 8](#) below lists the neutralizing antibody titer assay results to be assessed for each variant strains at specific visit for Cohorts 1 to 5.

**Table 7: Humoral immune response analysis against variants at selected timepoints for Cohorts 1 – 4 in the final study report**

	Cohort 1 (≥18-55 yoa) N=45 BNT162b2 + 5ug BNT162b4 - once N=15 BNT162b2	Cohort 2 (≥18-55 yoa) N=45 BNT162b2 + 10ug BNT162b4 - twice N=15 BNT162b2	Cohort 3a (≥18-55 yoa) N=45 BNT162b2 + 15ug BNT162b4 - 2nd dose XBB1.5 N=15 BNT162b2	Cohort 3b N=45 BNT162b2 + 15ug BNT162b4 - 2nd dose XBB1.5 N=15 BNT162b2	Cohort 4a (≥18-55 yoa) N=45 BNT162b2 + 30ug BNT162b4 - 2nd dose XBB1.5 N=15 BNT162b2	Cohort 4b N=45 BNT162b2 + 30ug BNT162b4 - 2nd dose XBB1.5 N=15 BNT162b2
V1 – Baseline (Pre-Dose 1)	WT, BA.4/5	WT, BA.4/5	WT, BA.4/5	WT, BA.4/5	WT, BA.4/5	WT, BA.4/5
V4 – Day 28 post-Dose 1	WT, BA.4/5	WT, BA.4/5	WT, BA.4/5	WT, BA.4/5	WT, BA.4/5	WT, BA.4/5
V6 – Month 6 post-Dose 1; pre-Dose 2	WT, BA.4/5	WT, BA.4/5	WT, BA.4/5, and XBB.1.5	WT, BA.4/5, and XBB.1.5	WT, BA.4/5, and XBB.1.5	WT, BA.4/5, and XBB.1.5
V9 – Day 28 post-Dose 2	NA	WT, BA.4/5	WT, XBB.1.5	WT, XBB.1.5	WT, XBB.1.5	WT, XBB.1.5

WT: Ancestral strain. NA: Not applicable.

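### SAP 6.1.3 averages duplicate post-baseline titers arithmetically although GMT and GMFR are log-scale; the plausible exposure is the pre-Dose 2 XBB.1.5 reference in Cohorts 3 and 4

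*SAP*

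**What the plan says.** SAP 6.1.3 states that when several valid observations fall in one window, "a single value will be chosen in the by-visit summary analyses based on the following rules". Before Dose 1 the rule picks a record and averages nothing: "the last available records prior to the date and time of the first dose of IMP will be selected". For post-baseline visits the highest toxicity grade decides; otherwise, "If the analysis values are numeric and the toxicity grades are identical or not available, the average (arithmetic mean) will be used". The documents assign no toxicity grade to neutralizing titers. SAP 6.6 adds a below-LLOQ substitution for titers but no rule for duplicates, so 6.1.3 applies.

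The titer endpoints are log-scale. Protocol 9.4.1: "Analysis of antibody titers will be performed on natural log scale and the results will be exponentiated back to original scale". SAP 6.1.1: "The GMs will be calculated as the mean of the assay results after making the logarithm transformation"; GMFRs are mean differences of logs.

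On the reference value, SAP 6.1.2 says "The same baseline definition will be used for the calculation of GMFR and seroresponse", meaning the last value before Dose 1. SAP 6.6.1.2 and 6.6.1.3 depart from this for XBB.1.5 in Cohorts 3 and 4, where fold rise and seroresponse run from the Dose 2 visit.

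On sampling, SAP Table 7 has one row, "V6 – Month 6 post-Dose 1; pre-Dose 2", and the footnote to SAP Table 4 reports any pre-Dose 2 draw at that timepoint whatever its window. The humoral draw is listed at both Visit 6 and Visit 7 (SAP Table 10), and Visit 7 may fall up to 30 days after Visit 6. Protocol Table 3 footnote t says assessments common to both visits need doing only once when the visits are combined. SAP Table 10 footnote t says Visit 7 is sampled only if Visit 6 was not.

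**The concern.** The arithmetic mean of two unequal titers is always above their geometric mean, and the gap widens with their ratio. Combining duplicates on the raw scale and then taking logs therefore does not match the planned analysis, and the error always has the same sign for the combined value.

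What that does to an endpoint depends on where the combined value sits. At the merged Month 6/pre-Dose 2 timepoint it raises the XBB.1.5 GMT at Dose 2. It is also the denominator of the XBB.1.5 fold rise, so it lowers the GMFR and raises the post-dose titer needed for a 4-fold seroresponse. These are secondary endpoints, and the seroresponse call is made participant by participant.

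**Working it through.** The plan gives no figure on this point, so there is nothing to reproduce. The averaging and log-scale rules come from the sections cited above. Two inputs are not in the documents and are assumed: the ratio r between two titers in one timepoint (2 to 4, with 8 as an extreme) and the share f of a group with two values (2% to 20%). In a planned BNT162b4 arm of 45, 2% is about one participant (0.02 × 45 = 0.9) and 20% is nine (0.20 × 45 = 9).

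**Step 1: one participant.** For titers x and r·x, the arithmetic mean is x(1 + r)/2 and the geometric mean is x√r. Their ratio is k = (1 + r)/(2√r).

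- r = 2: k = 3/(2 × 1.4142) = 1.061, an excess of 6.1%
- r = 4: k = 5/(2 × 2) = 1.25, an excess of 25%
- r = 8: k = 9/(2 × 2.8284) = 1.591, an excess of 59%

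**Step 2: the seroresponse bar.** With the averaged value as reference, a 4-fold rise means 4k-fold over the geometric mean: 4 × 1.061 = 4.24-fold at r = 2 and 4 × 1.25 = 5.0-fold at r = 4.

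Example: pre-Dose 2 XBB.1.5 titers of 100 and 200, post-Dose 2 titer of 580.

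- Arithmetic reference: (100 + 200)/2 = 150, and 580/150 = 3.87-fold, not a seroresponse
- Geometric reference: √(100 × 200) = 141.4, and 580/141.4 = 4.10-fold, a seroresponse

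For this pair, any post-dose titer from 4 × 141.4 = 565.7 up to just under 4 × 150 = 600 changes classification.

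**Step 3: the group.** If a share f has duplicates with the same r, the group GMT at that timepoint is multiplied by k^f, and a GMFR that uses it as reference by k^(−f).

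| f | r = 2: GMT factor | r = 4: GMT factor |
|---|---|---|
| 2% | 1.0012 | 1.0045 |
| 5% | 1.0029 | 1.0112 |
| 10% | 1.0059 | 1.0226 |
| 20% | 1.0118 | 1.0456 |

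The reference GMT is thus raised by 0.1% to 4.6%. The XBB.1.5 GMFR is multiplied by the reciprocal: 0.994 at r = 2, f = 10%; 0.978 at r = 4, f = 10%; and 1/1.0456 = 0.956 at the far corner. At f = 5% or less the shift is about 1% or less (0.3% at r = 2, 1.1% at r = 4).

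**Step 4: where duplicates can arise.** Unscheduled assessments are listed only (SAP 6.1.1), each other visit has one humoral draw, and the pre-Dose 1 baseline is a selected record. What remains is the merged Month 6/pre-Dose 2 timepoint, with Visits 6 and 7 on different days and both sampled. Only Dose 2 recipients have a Visit 7, so the one-dose control group is not exposed there.

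**The case against.** The strongest answer is that the rule may never reach a titer. SAP Table 10 footnote t leaves one draw across Visits 6 and 7, and both schedules say the visits should ideally coincide. SAP 6.1.3 bases analysis visits on the visits in the EDC system, where 6 and 7 are separate, and SAP 6.6.1.2 and 6.6.1.3 name the Dose 2 visit as the XBB.1.5 reference. The term analysis values is also undefined: if it means logged titers, their arithmetic mean already gives the geometric mean.

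Much of this stands. It makes duplicates uncommon and the effect small. It does not close the point. SAP 6.1.3 reports data according to the protocol's schedule, whose footnote removes the second draw only for a combined visit, and SAP Tables 4 and 7 merge the two draws into one timepoint. SAP 6.1.1 takes logs of assay results as a step of the calculation, so raw titers are the natural reading.

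A reader might infer that all titer endpoints are biased upward. The documents do not support that. The pre-Dose 1 baseline is never averaged, no sampling route to duplicates is described for the Day 28 visits, and the one plausible case pushes GMFR and seroresponse down. A reader might also count repeat assay runs as a source, but no visible text says that they enter the data as separate valid records. Nor is a shift above 10% supported: it would take about half of a group with 4-fold differences (1.25^0.5 = 1.118). Participants with a positive NAAT through the visit are excluded, which removes detected infection as a cause of wide differences.

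**Conclusion.** The averaging rule does not match the log-scale analysis wherever it meets raw duplicate titers: a 6% excess at a 2-fold difference and 25% at a 4-fold difference. The plausible exposure is confined to the pre-Dose 2 reference for XBB.1.5 in Cohorts 3 and 4, where it lowers the GMFR and can change individual seroresponse calls. Under the assumed 2–20% of participants with 2- to 4-fold differences, the group shift is about 0.1–4.6%, and about 1% or less if duplicates are at most 5%. This rests on analysis values meaning raw titers and on both visits having been sampled in some participants; neither is settled by the documents. The trial is descriptive, with no hypothesis tests, so no test result changes. Minor severity: a free improvement.

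**What to change.** Add to SAP 6.1.3 or 6.6: *For neutralizing titers and other assay results analysed on the log scale, multiple valid post-baseline values in one analysis timepoint are combined by their geometric mean, after the 0.5 × LLOQ substitution.* Keep the arithmetic mean for other variables. If log titers were always meant, the sentence only makes that explicit.

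Reconcile protocol Table 3 footnote t with SAP Table 10 footnote t on Visit 6/7 sampling, so that it is clear whether two pre-Dose 2 samples can exist.

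The cost is one SAP sentence and one line of dataset code. Doing it before database lock avoids deciding after the fact which participants count as responders.

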#### **6.1.4 Handling missing data**

Missing data, other than that described for medical history, AE, and concomitant medication below, will not be imputed.

For partial missing date of prior positive SARS-CoV-2 infection result date,

- If the day of the month is missing, the onset day will be set to the first day of the month (01MMMMYYYY).
- If the onset day and month are both missing, the day and month will be assumed to be 01 January (01JANYYYY).

For the purposes of assigning post-dose flag for AEs, partial or missing AE dates will be handled as follows:

- If the day of the month is missing, the onset day will be set to the first day of the month (01MMMMYYYY), unless it is the same month and year as the first dose of trial treatment. In this case, in order to conservatively report the event as post-dose, the onset date will be assumed to be the same as Dose 1 date.
- If the onset day and month are both missing, the day and month will be assumed to be 01 January (01JANYYYY), unless the event occurred in the same year as the trial treatment. In this case, the event onset will be assumed to be the day and month of the first dose of treatment in order to conservatively report the event as post-dose.
- A completely missing onset date will be assumed to be the date of first dose of trial treatment. Such AEs will be considered post-dose.
- For AEs with onset date the same as Dose 1 or Dose 2 date, but with missing time of onset, such AE will be considered post-Dose 1 or post-Dose 2. If the time is not missing, onset time should be considered when assigning the post-dose flag.
- If an AE has a partial stop date that is in the same month/year as the first dose of trial treatment, then the AE will be reported as post-dose. If an AE has a missing start date, then the AE will be reported as post-dose.

For the purposes of assigning prior or concomitant flag for medications/vaccinations, partial or missing medication/vaccination dates will be handled as follows:

End dates (for events not ongoing):

- If end day is missing and month/year are non-missing, then day is the minimum of treatment end date and the last day of the month (e.g. 31MMMYYYY).
- If end day/month are missing and year is non-missing, then day is the minimum of treatment end date and the end of the year (e.g. 31DECYYYY).
- If imputed end date is before the start date, use the start date as the imputed end date.
- If end date is completely missing, then the event is assumed as concomitant.

Start dates:

- If the start date year is missing, the start date is set to one day prior to treatment start date.
- If the start date year is less than the treatment start date year, then:
  - If the month is missing, the start date is assumed to be mid-year point (e.g. 01JULYYYY).
  - If the month is not missing (day and year available), the start date is assumed to be mid-month point (e.g. 15MONYYYY).
- If the start date year value is greater than the treatment start date year, then:
  - If the month is missing, the start date is assumed to be the year start point (e.g. 01JANYYYY).
  - If the month is not missing (day and year available), the start date is assumed to be the month start point (e.g. 01MONYYYY).
- If the start date year value is equal to the treatment start date year value, then:
  - If the month is missing or the month is equal to the treatment start date month, then the start date is assumed to be one day prior to the treatment start date.
  - If the month is less than the treatment start date month, the start date is assumed to be the mid-month point (e.g. 15MONYYYY).
  - If the month is greater than the treatment start date month, the start date is assumed to be the month start point (e.g. 01MONYYYY).

If the complete end date is available, and the start date assumed from the steps above is greater than the end date, then the assumed start date will be set to the end date.

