#### Cohorts 1 to 4:

OBJECTIVES	ESTIMAND*	ENDPOINTS
Primary objectives		
To describe the safety and tolerability of one and two doses of BNT162b4 + BNT162b2 Bivalent, one dose of BNT162b4 + BNT162b2 Monovalent (OMI XBB.1.5) as a booster, or one dose of BNT162b2 Bivalent alone at each applicable dose level (DL) in healthy adults aged 18 years and older, with and without evidence of prior SARS-CoV-2 infection who previously received at least three prior doses of an authorized RNA-based COVID-19 vaccine.	
For each DL cohort, the frequency of dosed participants with:
 

Solicited local reactions at the injection site recorded up to 7 d after every IMP dose.

Solicited systemic events recorded up to 7 d after every IMP dose.

Participants with at least one AE occurring up to 28 d after every IMP dose.

Participants with at least one SAE occurring up to 6 months after every IMP dose.

 
For each DL cohort, the percentage of dosed participants with:
 

Abnormal hematology or chemistry laboratory values 3 d (Dose 1 sentinel group only) and 7 d after every IMP dose.

Grading shifts in hematology or chemistry laboratory assessments between baseline and 3 d (Dose 1 sentinel group only) and 7 d after every IMP dose.

	

Solicited local reactions (pain, erythema / redness, induration / swelling)

Solicited systemic events (vomiting, diarrhea, headache, fatigue, myalgia, arthralgia, chills and fever)

AEs

SAEs

 

Hematology and chemistry laboratory parameters (see Section 10.3 of protocol)

OBJECTIVES	ESTIMAND*	ENDPOINTS
	For each DL cohort, the percentage of dosed participants with: 
 
• New ECG abnormalities 3 d (Dose 1 sentinel group only) and 7 d after every IMP dose.
 
	
 
• ECG abnormalities consistent with probable or possible myocarditis or pericarditis as defined in the protocol
 

Secondary objectives		

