### 6.5.1.3 Adverse events

Non-serious AEs will only be collected as of first IMP dose administered while SAEs need to be recorded upon awareness starting once informed consent is given. For Cohorts 1 to 4, AE collection will start from Visit 0 and continue until Visit 4 (i.e., until 1 month follow-up post-Dose 1), and (for participants who consent to a second dose of IMP after issue of

protocol version 5.0) restart from Visit 7 and continue until Visit 9 (i.e., until 1 month follow-up post-Dose 2). For Cohort 5, AE collection will start from Visit 0 and continue until Visit 9 (1 month post-Dose 2). AESIs, SAEs, AEs that lead to trial participant discontinuation or withdrawal, and all AEs linked to confirmed COVID-19 cases will be recorded up to the last planned visit for participants who consent to a second dose of IMP. For participants in Cohorts 1 to 4 completing Dose 1 only, recording will continue until Visit 6 (6 months post-Dose 1). For participants in Cohort 5 completing Dose 1 only, recording will continue until the last scheduled visit (5 months post-Dose 1).

Summary tables will include AEs reported from each IMP administration up to 28 days after each IMP administration, SAEs and AESIs occurring from IMP Dose 1 up to 6 months after each IMP administration for participants in Cohorts 1 to 4 and SAEs occurring from IMP Dose 1 up to 3 months after last IMP administration for participants in Cohort 5. AEs leading to IMP discontinuation or trial withdrawal will be listed, and summarized when at least 10 events in all participants have been reported.

AEs/SAEs post-Dose 1 will be summarized by treatment group post-Dose 1 based on the Safety Set. AEs/SAEs post-Dose 2 will be summarized by treatment group post-Dose 2 based on Dose 2 Safety Set.

All AEs will be coded using the most recent version of the MedDRA® coding system and graded for severity using FDA guidance for “[Toxicity Grading Scale for Healthy Adult and Adolescent Volunteers Enrolled in Preventive Vaccine Clinical Trials](#)”. No imputation for missing grades will be performed.

If an AE is reported more than once for the same participant for a SOC / PT the AE will be counted once for this SOC / PT for the specified reporting period.

All AE (from post-dose) summary tables will be sorted alphabetically by SOC and PT within SOC, unless specified otherwise.

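### The AE missing-day rule protects only the Dose 1 month, so an AE dated only to the Dose 2 month is normally imputed before Dose 2 and drops out of the post-Dose 2 28-day tables (wrong as written, small effect)

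*SAP*

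**What the plan says.** The relevant bullets in SAP 6.1.4 open with "For the purposes of assigning post-dose flag for AEs, partial or missing AE dates will be handled as follows". For a missing onset day, the default is the first of the month, "unless it is the same month and year as the first dose of trial treatment". That is the one exception, and under it, "in order to conservatively report the event as post-dose, the onset date will be assumed to be the same as Dose 1 date".

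The other AE bullets in that section are:
- Missing day and month: 1 January, or the Dose 1 date if the year is that of trial treatment.
- Completely missing onset: the Dose 1 date.
- Stop date: an AE with a "partial stop date that is in the same month/year as the first dose of trial treatment" counts as post-dose. A further sentence calls an AE with a missing start date post-dose, without saying which dose.
- Missing time: "For AEs with onset date the same as Dose 1 or Dose 2 date, but with missing time of onset", the event is post that dose. This is the only bullet that names Dose 2, and it needs a complete onset date.

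The tables need the two doses kept apart. A primary estimand in SAP 1.1 is "Participants with at least one AE occurring up to 28 d after every IMP dose". SAP 6.5.1.3 states "Summary tables will include AEs reported from each IMP administration up to 28 days after each IMP administration" and summarizes post-Dose 2 events separately on the Dose 2 Safety Set.

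**The concern.** The rule aims to be conservative: when in doubt, count the event as following vaccination. It does this for Dose 1 and the reverse for Dose 2. An AE known only to have begun in the Dose 2 month is placed on the 1st, normally before Dose 2, and so leaves the table it most likely belongs to. In Cohorts 1 to 4 the imputed date usually falls in a period when non-serious AEs were not being collected, because collection stops at Visit 4 and restarts at Visit 7. At stake is a small downward bias in the post-Dose 2 any-AE rate and in the tables by preferred term.

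**Working it through.** The plan gives no figure to reproduce on this point. The check applies the rule to dates.

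**1. One case.** Dose 1 on 10 March 2023, Dose 2 on 14 September 2023, true onset 18 September recorded as September 2023. The rule gives 1 September: 13 days before Dose 2 and 175 days after Dose 1. The AE is in neither 28-day table.

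**2. Share displaced, given a missing day.** Assumptions: every Dose 2 date from 2023 to 2026 equally likely (1,461 dates), and onset equally likely on days 0 to 28 after Dose 2 (29 values).
- Pairs: 1,461 × 29 = 42,369.
- Onset in the Dose 2 month: 54.0%.
- Of these, first of month earlier than Dose 2: 93.9%. The remainder are cases with Dose 2 on the 1st.
- Displaced overall: 0.540 × 0.939 = 0.507, about 51%. Retained: 49.3%.
- Onsets in the following month are imputed to its first day and all stay in the window.

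The result depends on the onset assumption. If onsets are uniform over 0 to 14 days the share is 73.7%, and over 0 to 7 days 85.2%.

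**3. Where displaced non-serious AEs go.**
- Cohorts 1 to 4: the visit windows in the SAP 8.4 schedule (Visit 6 at day 180, −10 to +30; Visit 7 up to 30 days later) put Dose 2 on trial days 170 to 240, which is 169 to 239 days after Dose 1. The first of the month is 1 to 30 days earlier, so imputed onset is 139 to 238 days after Dose 1. This is never within 28 days, so the AE is in neither table.
- Cohort 5: Dose 2 is at 2 months. Assuming 61 ± 7 days (54 to 68), imputed onset is 24 to 67 days after Dose 1. Weighted by onset, about 0.4% of such AEs reach the post-Dose 1 table. With Dose 2 at exactly 61 days the range is 31 to 60 days and none do.

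**4. SAEs and AESIs.** In Cohorts 1 to 4 the window is 6 months after each dose, or 6 × 30.4375 = 182.6 days. A displaced event leaves the post-Dose 2 table. The onset-weighted share imputed within 182.6 days of Dose 1 is 34.5% for Dose 2 uniform over trial days 170 to 240, 59.7% for days 170 to 210 (Visits 6 and 7 on the same day), and 100% for day 180. In Cohort 5, SAP 6.5.1.3 also tabulates SAEs from Dose 1 through 3 months after the last dose, so a displaced SAE stays in that combined table.

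**5. Effect of one participant** with no other AE in the window, if all receive Dose 2: 1/45 = 2.2 points, 1/20 = 5.0 (Cohort 5), 1/90 = 1.1 (3a and 3b pooled, or 4a and 4b pooled). The shift is larger if fewer receive Dose 2.

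**The case against.** The strongest reply is that the trigger hardly occurs. Protocol 10.4.3 requires start date and time of onset in the CRF, and Protocol 10.2.1 has discrepant data queried. After Dose 2, AEs are recorded at Visit 8 (7 to 9 days) and Visit 9 (25 to 31 days), so recall between them spans 16 to 24 days. SAEs are reported within 24 hours of awareness. Solicited reactions captured in the e-diary do not pass through this rule. This stands, and it is why the point is minor. It limits how often the rule is applied but does not make the rule right.

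A second reply is that SAP 6.5.1.3 speaks of data reported in each period, so an AE recorded after Dose 2 would count there anyway. This does not hold: SAP 6.1.4 assigns the post-dose flag from the onset date, and the estimand counts AEs by when they occur. Nor does the sentence on missing start dates help. An event imputed between the doses is already post-dose relative to Dose 1.

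Two stronger readings are tempting and unsupported. A reader might infer that half of post-Dose 2 AEs would vanish. The 51% applies only to AEs with a missing day, and the documents give no rate for those. A reader might also want one percentage for SAEs moved to post-Dose 1. The share runs from about 34% to 100% with the assumed Dose 2 timing. SAP 6.5.1.3 also leaves it unsettled whether an SAE imputed after 6 months but before Dose 2 is tabulated: one sentence limits the interval to 6 months, while another assigns everything after Dose 1 and before Dose 2 to the Safety Set summary.

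**Conclusion.** The rule is wrong as written, with a small effect. Unless Dose 2 was on the 1st, a month-only AE in the Dose 2 month leaves the post-Dose 2 28-day tables. In Cohorts 1 to 4 a non-serious AE then appears in neither 28-day table, and in Cohort 5 all but about 0.4% do the same. In Cohorts 1 to 4 an SAE or AESI leaves the post-Dose 2 table and may be counted as post-Dose 1; a Cohort 5 SAE leaves the post-Dose 2 table but not the combined one.

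That follows from the text. The 51% rests on uniform Dose 2 dates and onsets and is conditional on a missing day; the 0.4% also rests on Dose 2 at 54 to 68 days. The absolute effect cannot be computed. A reader might infer that the safety conclusions are unreliable, but the documents do not support that: the error is confined to summary tables, every AE remains in the listings, and no hypothesis test depends on it. Severity: minor.

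**What to change.** Add to SAP 6.1.4: *If the onset day is missing and the month and year equal those of Dose 2, onset will be set to the Dose 2 date, unless the stop date or the visit at which the AE was recorded shows that it began before Dose 2.* In the enumeration above, this keeps 100% of the displaced and non-displaced events in the post-Dose 2 window, against 49.3% as written.

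Extend the same logic to the bullets on missing day and month, completely missing onset, and partial stop date, which also refer only to the first dose. There, use the visit at which the AE was recorded to assign it to Dose 1 or Dose 2.

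The cost is a few lines of SAP text and a small programming change. The downside is that a few pre-Dose 2 events may be counted as post-Dose 2, in line with the rule's stated aim. For non-serious AEs in Cohorts 1 to 4 this should be rare, given the gap in collection between Visits 4 and 7. In Cohort 5 collection is continuous, so the check on the recording visit matters more.
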